## 2. INTRODUCTION

### 2.1. Study Background and Rationale

Catheter-associated urinary tract infections (CAUTI) are one of the most common hospital-acquired infections (HAI), accounting for more than 15% HAIs in the United States. On October 1, 2008, the Centers for Medicare & Medicaid Services (CMS) stopped reimbursing hospitals for treatment of preventable HAIs. Subsequently, hospitals have implemented CAUTI prevention bundles to reduce these largely preventable, costly, and morbid infections. Guidelines for the prevention of CAUTI focus on the following four aspects of prevention: appropriate device utilization, aseptic insertion technique, proper care/maintenance of the catheter, and timely removal of the urinary catheter.

Several interventions seeking to reduce CAUTIs have studied the impact of chlorhexidine gluconate (CHG) bathing in the intensive care unit (ICU) but have not found a significant effect. Though one study did find a significant reduction in high-level (>50,000 colony-forming units) candiduria and any level of bacteriuria with CHG bathing, the study did not evaluate the impact on CAUTI rates, nor did it investigate the effect of perineal care and maintenance following catheter insertion. Additionally, the expanded use of CHG carries with it the potential for development of CHG-resistant bacteria which could compromise its use for surgical site infection prevention.

Few studies have exclusively investigated the effect of catheter care and maintenance on CAUTI rate. ReadyCleanse® meatal and perineal cleansing cloth by Medline Industries, Inc. (hereafter ReadyCleanse®) is a set of five prepackaged cloths including a gender-specific, five-step cleansing process clearly described on label that is designed to minimize transfer of bacteria to the patient during catheter care. Moreover, it does not contain ingredients that are bactericidal or bacteriostatic, thereby reducing the risk of compromising interventions such as CHG prior to surgery due to overuse. Thus, ReadyCleanse® provides an easy-to-use, efficient, and standardized means of conducting catheter care that may significantly reduce CAUTI rates compared to standard-of-care.

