#### 6.3.2. Compliance with Intervention/Auditing

During the study, random on-site observations of perineal care will be performed by research study coordinators. The study coordinators will directly observe the performance of perineal care for 10 IUC patients at each hospital and adherence to the written protocol will be determined. For sites that have adherence rates below the 90th percentile, we will acquire an additional 10 more observations to reduce the effect of sampling error. Observations of perineal care will be performed during the first seven months of the data collection portion of the intervention, with a goal that all audits are complete within three months.

Due to extension of the study, the second (and subsequent, if required) set of audits will be executed by Medline Industries, Inc., in corroboration with NorthShore University Health System.

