## 8. STATISTICAL CONSIDERATIONS

### 8.1. Sample Size Determination

The primary outcome will be measured as number of CAUTIs per 1000 catheter days. Given this type of data, a Poisson regression model will be used to model CAUTI incidence, with the dichotomous predictor variable pertaining to the intervention serving as the critical test for the hypothesis. To determine how many catheter days would be needed to adequately power the study, a power analysis was conducted using G\*Power 3.1.9.2, with the following parameters:

- **Baseline CAUTI Rate:** 0.89/1000 catheter days (entered as .00089/day)
  - Baseline rate reflects CAUTI rate for NorthShore University Health System in 2016.
- **Hypothesized reduction in CAUTI:** 50%
- **Alpha:** 0.05 (one-tailed)
- **Power:** 80%
- **Mean Exposure:** 1 day (the actual exposure will vary by participant, but entering 1 day can be used to determine number of catheter days rather than number of participants).
- **R^2 other X:** 0%
- **X distribution:** Binomial
- **X parm II:** 0.5

The result from this analysis indicated that 83,426 catheter days would be needed to adequately power the study at 80%. NorthShore Hospital University System averages approximately 32,000 catheter days annually, which can be reduced to 2,667 per month. Thus, total number of catheter days required for collecting retrospective data and prospective data would be 85,344 catheter days. The 42,672 (85,344-catheter days/2) catheter days of prospective data in comparison to a similar number of catheter days of retrospective data will provide data required for conducting the analysis.

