## 8.2. Statistical Analysis

### 8.2.1. Primary Endpoint

The primary endpoint will be the comparison of CAUTI rates during the intervention period compared to the retrospective control period. This will be tested by modeling the likelihood of developing a CAUTI as a function of intervention status using Poisson regression, with the number of catheter days serving as the offset. A significant value for the parameter representing the intervention will serve as the test for the impact of the intervention. Formally, the hypothesis is:

$$H_0: \beta_1 \geq 0$$

$$H_1: \beta_1 < 0$$

Where  $\beta_1$  represents the beta-parameter for the dichotomous predictor variable pertaining to the intervention, with the retrospective control group coded as 0 and the prospective intervention group coded as 1.

The 95% confidence interval for the incidence rate ratio will also be presented.

Given that the retrospective and prospective portions of the study cover a significant period of catheter days, it is not expected that the two groups will vary on demographic variables or other key variables such as length-of-time the catheter is inserted, hospital unit during admission, etc. Thus, testing the incidence rate ratio will be sufficient for determining if there is a significant difference in the CAUTI rate between the two time periods.

In the event of over-dispersion of the data, negative binomial regression may be implemented to account for the over-dispersed data. Missing data on the primary endpoint is not anticipated to be a concern, given that government reporting requirements dictate that CAUTI rates be reported, which only requires an analysis of catheter days and number of CAUTIs. Participants who are discharged with an IUC or who expire during their admission will have their catheter days as well as any infections that occurred prior to discharge or death counted in the analysis.

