#### 9.1.7. Data handling and Record Keeping

##### 9.1.7.1 Data Collection and Management Responsibilities

Data collection is the responsibility of the clinical trial staff at the site under the supervision of the site investigator. The investigator is responsible for ensuring the accuracy, completeness, legibility, and timeliness of the data reported.

All source documents of any kind (electronic, paper, etc.) should be completed in accordance with Good Documentation Practices (GDP) to ensure accurate interpretation of data. CRFs will be created for each subject for the prospective portion of the study. CRFs will be generated retrospectively only for patients that developed a CAUTI. The CRF for each subject will be populated from the subject's EHR. The CRA will verify the data entered into the CRF with the site source regardless of the type of source. The site will be responsible for developing a written process that ensures the CRA is able view the source data.

Data from the CRFs will be entered by NorthShore study staff into a Microsoft Excel spreadsheet for statistical analysis. Data in the Excel database will be transferred to and analyzed with SAS, which allows for internal quality checks, such as automatic range checks, to identify data that appear inconsistent, incomplete, or inaccurate. Medline Industries, Inc. will be responsible for overseeing final data analysis and confirmation of results.

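### The unadjusted rate ratio rests on equal dwell time and unit mix in the two periods; the planned control data cannot check the first, and section 4.3 contradicts the second.

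*Combined protocol and SAP*

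**What the plan says.** Section 8.2.1 fits a Poisson model with intervention status as the only named predictor and catheter days as the offset. It expects no difference between the periods on demographics or "other key variables such as length-of-time the catheter is inserted, hospital unit during admission", gives the large volume of catheter days as the reason, and concludes that the rate ratio is sufficient.

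The data differ by period. Section 6.3.1.1 collects insertion date, removal date, catheter days, hospital and room for every prospective catheterised patient. For control, section 6.3.1.2 uses a CAUTI rate that is already held, plus case report forms for patients who developed a CAUTI. Section 9.1.7.1 confirms this: "CRFs will be generated retrospectively only for patients that developed a CAUTI".

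Section 4.3 excludes one hospital's ICU from the control dataset, because it had recently changed its method of catheter care, but pools that unit's prospective data with the rest.

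Section 4.1 says the baseline prevention bundle continues with no new interventions, and acknowledges that a retrospective control has limitations. It plans no check on dwell or unit.

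**The concern.** A large number of catheter days makes each period's rate more precise. It does not make two calendar periods alike. If the types of catheter or the units differ systematically, more days only estimate the biased contrast more precisely.

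The plan names dwell as a key variable and then collects it for one period only. Dwell among infected controls cannot stand in for the control population, because those patients are selected on the outcome. The unit half of the same sentence is contradicted by section 4.3.

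At stake is the reading of the primary result. Section 4.1 takes a significant reduction as evidence that the cloths and process likely reduce CAUTI. If daily risk rises with dwell, a shift towards shorter dwell would lower the rate with no effect of cleansing, and a shift towards longer dwell would hide a real benefit.

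**Working it through.** **1. The plan's own figure.** Inputs from section 8.1: control rate 0.00089 per catheter day, 50% reduction (0.000445), one-sided alpha 0.05, power 80%, equal split. The rate-difference formula for the total is

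2 × (1.645 + 0.842)² × (0.00089 + 0.000445) / (0.00089 − 0.000445)² = 83,360.

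The pooled two-proportion formula gives 83,304, which is 0.15% below the stated 83,426. The figure reproduces, although the exact G*Power procedure cannot be identified: other one-sided Poisson formulas give 66,968 to 86,752. Also 2,667 × 16 = 42,672 per period.

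**2. Expected events.** Control: 42,672 × 0.00089 = 38.0. Intervention under a halving: 19.0. Total: about 57. With 38 control events, a one-sided Wald test needs 24 or fewer intervention events (24/38 = 0.63).

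**3. What is missing.** A rate by catheter-day band needs events and catheter days in each band.
- Events by band are available in both periods: the case report form for CAUTI patients records insertion date and CAUTI date.
- Catheter days by band are available for the intervention only.
- Control catheter days by band are not collected.

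**4. When this matters.** Let a and b be the shares of control and intervention catheter days that fall after day 4, and k the daily risk after day 4 relative to days 1–4. With no effect of cleansing,

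rate ratio = [(1 − b) + k·b] / [(1 − a) + k·a].

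If k = 1 the ratio is 1 for any a and b, because the offset removes the change in dwell completely. If a = b it is 1 for any k. Both a shift in mix and a varying daily risk are needed.

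**5. Illustration.** The documents give neither the dwell distribution nor the hazard, so a, b and k are assumptions. Take a = 0.40. The rejection rate comes from enumerating the one-sided 5% Wald test over Poisson counts with 38.0 expected control events.

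| b | k | Rate ratio, no true effect | Test rejects |
|---|---|---|---|
| any | 1 | 1.00 | 4.9% |
| 0.30 | 2 | 1.30/1.40 = 0.93 | 9% |
| 0.30 | 3 | 1.60/1.80 = 0.89 | 12% |
| 0.20 | 2 | 1.20/1.40 = 0.86 | 16% |
| 0.20 | 3 | 1.40/1.80 = 0.78 | 26% |
| 0.50 | 2 | 1.50/1.40 = 1.07 | below 5% |
| 0.50 | 3 | 2.00/1.80 = 1.11 | below 5% |

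In the last row, a true halving would appear as 0.5 × 1.11 = 0.56, and power by the same enumeration falls from about 82% to 71%.

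**6. Cross-check with other assumed shapes** (geometric dwell). With no risk on days 1–2 and constant risk after, shortening mean dwell from 5 to 4 days gives (0.75/0.80)² = 0.88 and 13% rejection; from 4 to 3 days, 0.79 and 25%. With risk rising linearly by day, the ratios are 4/5 = 0.80 (23%) and 3/4 = 0.75 (31%). With constant risk the ratio is 1.00 and the rejection rate about 5%.

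**7. Unit.** This part needs no assumption. One ICU contributes catheter days to the intervention and none to control, so unit mix differs by design. The size of any resulting bias depends on that unit's rate and share of days, which the documents do not give.

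**The case against.** The best defence is the offset. A reader might infer that any change in catheter use could pass for an effect of the cloths. The documents do not support that: dividing by catheter days removes changes in total use, and changes in dwell if daily risk is constant. This stands, and it limits the concern to a shift in dwell mix combined with a risk that varies by catheter day.

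The documents also show no evidence that dwell changed. Section 4.1 says the bundle is unchanged. That is a real but partial safeguard, since it is an intention and not a measurement. Three tempting inferences fail:
- Section 2.1 lists "proper care/maintenance of the catheter, and timely removal of the urinary catheter" among the aspects of CAUTI prevention. This is general background and does not show that removal practice differed between periods.
- Training might be thought to shorten dwell. Section 6.1 describes a product-use video, package instructions and handouts, with nothing on catheter indication or removal.
- The wording "Due to extension of the study, the second (and subsequent, if required) set of audits" in section 6.3.2 might suggest slower accrual and hence a change in dwell. No cause of the extension is given, and slower accrual would not show shorter dwell.

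A reader might also want CAUTIs per patient-day. That is a different estimand, more sensitive to catheter use than the present one, and section 3 defines the endpoint per 1000 catheter days.

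Two practical objections stand in part. The version 2.0 entry in the Document History says some variables could not be collected retrospectively, without naming them, so retrieval is not guaranteed. And about 57 expected events split by band and unit will give an imprecise adjusted estimate.

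**Conclusion.** The concern holds in a limited form. The stated reason for relying on an unadjusted rate ratio cannot be checked for dwell with the planned control data, and it is contradicted for unit by section 4.3. That much follows from the documents alone.

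Whether the rate ratio is biased by dwell, and in which direction, is unknown. Under the assumed inputs the rate ratio with no true effect runs from 1.00 down to 0.78, with rejection from 5% to 26%. The top of that range needs long-dwell days to halve as a share and later-day risk to be three times earlier risk. A shift to longer dwell gives up to 1.11 and costs about 11 points of power (82% to 71%). These figures show sensitivity and do not estimate what happened. The sample size and the primary test are not in question. The change is worth making because a bias of this size matters with about 38 and 19 expected events.

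**What to change.** In section 6.3.1.2, add one extract from the electronic data warehouse already named there: insertion date, removal date and unit for all eligible catheterised patients in the control period, or catheter-day totals by dwell band and unit. No case report forms are needed for uninfected controls.

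In section 8.2.1, replace the sentences that expect no difference and call the rate ratio sufficient. Put in their place:
- a reported comparison of dwell and unit mix by period;
- a prespecified sensitivity Poisson rate ratio adjusted for catheter-day band and unit.

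Keep the primary test unchanged. Once unit is in the model, the ICU with no control data adds nothing to the intervention contrast, so the sensitivity result also shows what pooling that unit does. Prospective unit would have to be derived from the hospital and room already recorded.

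The cost is a small extraction effort and a few extra result rows, with an adjusted estimate that will be imprecise. If the dates cannot be retrieved, state alongside the conclusion that similarity of dwell is unverified, and that unit mix differs because of the excluded ICU.

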### 8.2.2. Secondary Endpoint

The secondary endpoint will be an analysis of bacteria in the urine, comparing a random sub-sample of the study sample during the intervention to a random sub-sample of participants during the beginning of the Education Intervention. Samples of urine from the Education Intervention and those taken during the intervention will be compared in two ways. The number of individual bacterial species isolated from the cultures will be compared between the two groups, as well as cfu/ml of bacteria present, which will be quantified as follows:

1. No bacterial growth
2. 100-500 cfu/ml
3. 500-10,000 cfu/ml
4. 10,000-50,000 cfu/ml
5. 50,000-100,000 cfu/ml
6.  $\geq 100,000$  cfu/ml

Parametric or non-parametric measures, depending on the normality of the distribution, will be used to compare the two groups' mean values on these two measures, with the hypothesis that use of ReadyCleanse® may reduce the amount of bacteria in the urine, providing a mechanistic account of how it may reduce CAUTI.

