#### 6.3.1.1.2. Urine culture

Quantitative urine cultures will be obtained from patients with IUC in-situ for at least 5-7 days. Twenty randomly selected IUC specimens will be obtained during the Educational Intervention period and another 20 samples during the study. Urine will be collected by the research coordinator from the IUC and transported to the research microbiology laboratory at NorthShore in a sterile, leak-proof container labeled with patient's study ID number. 1ul and 10ul loops will be used to streak a blood agar plate and MacConkey agar plate. Both plates will be incubated at 35°C in a non-CO2 incubator and inspected for growth of bacteria after 18-24 hours of incubation. Individual bacterial colonies will be identified using Matrix Assisted Laser Desorption/Ionization-Time of Flight (MALDI-TOF) mass spectrometry and quantity of organism calculated. The CRF specific to this portion of the study is provided in Appendix 11.6. Finally, all participants who develop a CAUTI will have a urine culture performed to determine the causative bacteria and susceptibility pattern.

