11.6. Case Report Form: Urine Sub-Analysis

R17-019 Case Report Form: Urine Sub-Analysis			Completed by:		
Demographic Information					
1. Participant Number:		2. Age:	3. Sex: Male  Female 		4. Race (may select more than one): Black  White  Asian  Hispanic  Other 
5. Hospital: E:  G:  S:  H: 			6. Room Number:		
Study Data					
7. Bacteria present in sample			 No growth	 10,000-50,000 cfu/ml	
			 100-500 cfu/ml	 50,000-100,000 cfu/ml	
			 500-10,000 cfu/ml	 > 100,000 cfu/ml	
			Organism(s) identified:		

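### Section 8.2.2 leaves the 20 v 20 urine comparison unadjusted and its test open, although form 11.6 records sex: a modest loss that SAP wording can recover

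*Combined protocol and SAP*

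**What the plan says.** Section 8.2.2 describes the only secondary analysis as "comparing a random sub-sample of the study sample during the intervention to a random sub-sample of participants during the beginning of the Education Intervention". Section 6.3.1.1.2 gives the numbers: "Twenty randomly selected IUC specimens will be obtained during the Educational Intervention period and another 20 samples during the study". No pairing is described, so I read these as two independent groups of patients, though the text does not say so outright.

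Two measures are used: "The number of individual bacterial species isolated from the cultures will be compared between the two groups, as well as cfu/ml of bacteria present". The cfu/ml result falls in one of six numbered bands, from "No bacterial growth" (band 1) to 100,000 or more (band 6). Form 11.6 records it, under "Bacteria present in sample", only as a ticked band, with no field for a raw count.

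For both measures the plan compares the groups' "mean values on these two measures". The method is left open: "Parametric or non-parametric measures, depending on the normality of the distribution, will be used to compare the two" groups. Section 8.2.2 gives no named test, normality criterion, covariate, significance level, sidedness, effect estimate or confidence interval. The one-tailed 0.05 in Section 8.1 belongs to the primary endpoint. Form 11.6 records age, sex and hospital for every specimen, and Section 8.2.2 uses none of them.

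**The concern.** The two periods are not randomised and each contributes only about 20 specimens, so the groups can differ in sex or hospital by chance or because case mix shifts. Section 8.2.1 defends an unadjusted primary comparison by the large number of catheter days in each period. That argument cannot carry over to 40 specimens, and Section 8.2.2 puts nothing in its place.

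The documents give some reason to think these factors matter. The cleansing procedure in Appendix 11.1.2 is sex-specific. Section 4.3 says the ICU of one hospital had already changed its catheter-care method.

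The summary is also weak. A mean of codes 1 to 6, for bands of very unequal width, has no unit and cannot be read as cfu/ml. With no estimate or interval planned, the reader would get a p-value from a test chosen after the data are seen. Section 3 offers this endpoint as a possible mechanistic explanation of any fall in CAUTI, and that explanation is what an unbalanced draw could create or hide.

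**Working it through.** The documents give no basis for 20 v 20, so there is no planned figure to reproduce.

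**1. Chance of a sex imbalance.** Assume half the eligible patients are women; the documents do not say. With X and Y independent Binomial(20, 0.5), P(|X − Y| ≥ m) is the sum of C(20,i)·C(20,j)/2^40 over all i, j with |i − j| ≥ m.
- 4 or more: 0.268
- 6 or more: 0.081
- 8 or more: 0.017

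With 40% or 60% women, the same sum with those binomial weights gives 0.258, 0.075 and 0.014.

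**2. What an imbalance does.** Assume, for illustration only, band probabilities for codes 1 to 6 of .20, .05, .10, .10, .10, .45 in women and .45, .10, .10, .10, .05, .20 in men, with no cloth effect. The mean codes are:
- women: .20 + .10 + .30 + .40 + .50 + 2.70 = 4.2
- men: .45 + .20 + .30 + .40 + .25 + 1.20 = 2.8

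A gap of g women shifts the difference in group means by 1.4 × g/20. Rejection rates below are two-sided at 5%, with 6,000 simulated trials per row. The planned rule is taken as a Shapiro-Wilk check followed by a t-test or rank test.

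| Women in the two groups | Shift in mean code | Planned rule | Sex-stratified rank test |
|---|---|---|---|
| 10 v 10 | 0 | 3.5% | 4.6% |
| 12 v 8 | 0.28 | 5.4% | 4.5% |
| 13 v 7 | 0.42 | 8.0% | 4.7% |
| 14 v 6 | 0.56 | 11.7% | 4.9% |

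**3. Overall error.** The table is conditional on the split. When the sex counts are drawn at random with the same mix in both periods, the planned rule rejects 4.7% of the time (10,000 runs), and 4.9% in a separate run. The low rate at 10 v 10 offsets the high rates in the tail.

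**4. Precision.** Take an example effect in which 60% of intervention specimens drop two codes, under the same assumed sex effect. Power, planned against stratified, was:
- sex balanced: 20.5% v 24.5% in one simulation (3,000 runs) and about 16% v 22% in another
- sex counts random: about 20% v 23%

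The two balanced results differ by more than simulation error (√(0.2 × 0.8/3,000) = 0.7 points), so the rough range is the result, not any single figure.

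**5. The normality step.** Under three other assumed distributions with no effect, the check rejected normality in 89% to 100% of samples, so the rule nearly always ends at the rank test. Its two-sided error was 4.5% to 5.1%. At a proportional odds ratio of 4, the t-test and rank test disagreed on significance in 5% to 10% of runs, so naming the test in advance still has value.

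**6. What 20 v 20 can show.** A two-sided 5% t-test has 80% power only for a difference of about 0.91 SD. For 0.5 SD, power is about 35% (normal approximation).

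**The case against.** The strongest reply is that both groups are specified as random samples. If the periods share the same sex mix, an imbalance is pure chance and the unadjusted test already allows for it. That stands. A reader might infer from the table that the planned test has a false-positive rate of up to 12%. The documents do not support this: the overall rate is about 5%, the 14 v 6 split needs a gap of 8 women, and a gap that large or larger has a chance of 1.7%. At the more likely gap of 4 the rate is 5.4%. The sex effect behind these figures is a single assumption with no source in the protocol, and nothing was calculated for hospital or age.

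A reader might also infer that picking the test by normality inflates error. It does not; the plan in practice leads to a rank test, which is valid whatever the band widths. The unequal widths spoil the mean as a summary, not the test.

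The stakes are also low. Section 3 says only that the endpoint may explain a reduction, and Section 4.1 rests the efficacy conclusion on CAUTI rates. A larger difficulty is the baseline itself. Section 6.2 has trained staff already using the cloths during the Educational Intervention, when the first 20 specimens are taken, while Section 3 describes that sample as collected before the intervention. Adjusting for sex cannot repair this.

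What remains is narrower. The test is unnamed, no estimate is planned, a recorded covariate that could sharpen the comparison is unused, and the single draw has no protection against a chance imbalance or a real shift in sex mix between periods. A real shift would not average out.

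**Conclusion.** The point holds as one of efficiency and prespecification. Under the assumed sex effect, the loss is about 3 to 6 percentage points of power (16% to 20% against 22% to 24%), and the endpoint has low power either way. The protection forgone concerns a gap of 4 or more women in about 27% of draws, 6 or more in 8%, and 8 or more in 1.7%, assuming half are women. The overall false-positive rate is not inflated if sex mix is the same in both periods, and the normality check is redundant.

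It would go too far to say that adjustment makes the two periods comparable. It deals with sex mix only, and form 11.6 has no catheter-days field, so time in situ cannot be adjusted for from that form alone. The primary endpoint is unaffected. The change is worth making because it is nearly free.

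**What to change.** In Section 8.2.2, drop the normality check and prespecify one primary analysis per measure: a rank test stratified by sex (van Elteren), with its level and sidedness stated. For cfu level, report alongside it the odds ratio for period with 95% CI from a proportional-odds model adjusted for sex, in place of a difference in mean codes. The rank test supplies the p-value and the odds ratio the estimate. Use age and hospital only in sensitivity analyses, since 40 specimens support few covariates.

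Keep the random selection of specimens. Matching the second 20 to the first by sex and hospital would spread 20 specimens over 2 × 4 = 8 cells and replace the random sampling that Sections 3, 6.3.1.1.2 and 8.2.2 specify.

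The cost is SAP wording and a few lines of SAS, with no new data. The downside is one or two degrees of freedom in 40 specimens, and other differences between the periods remain.
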